7.0 Sharing of Results with Participants

PROTOCOL TITLE: Prospective Randomized controlled trial comparing liposomal bupivacaine to bupivacaine Interscalene blocks for total shoulder arthroplasty surgery

VERSION DATE: 7/6/2020

Results will not be shared with participants.

8.0 Study Population

Inclusion Criteria: All adult patients aged greater than 18 years of age that are undergoing total or reverse total shoulder arthroplasty

Exclusion Criteria: Patients with allergy to local anesthetics, daily use of opioids for more than 3 weeks prior to surgery, patient refusal and those who have opted out of research, patients with coagulopathy, non-english speaking patients, and those who do not have access to a telephone.

Screening: Patients will be screened at their preoperative visit either in the surgeon's office, pre assessment center, or preoperative area.

9.0 Vulnerable Populations

Vulnerable Populations: No vulnerable populations will be included in the study.

10.0 Local Number of Participants

Local Number of Participants to be consented: 90 patients as we expect a drop out or loss to follow up of 20%.

11.0 Local Recruitment Methods

Recruitment Process: Patients will be recruited from the group of adult surgical patients at the University of Minnesota undergoing TSA and receiving an interscalene block. Patients will be approached at the preoperative assessment clinic at the Clinic and Surgery Center if possible by a research staff member to determine their interest in participation. If they decide to be a participant they will be consented and given a copy of their consent form for their records and a consent will be scanned and placed into EPIC. If they need additional time to consider enrollment, they will be asked if we can reach out to them by phone the night before surgery or if we should revisit the study with them on the day of surgery. If the patient is unable to be consented prior to day of surgery, the research staff will approach them in the preoperative surgical area. These patients will have significant time to review the study with research staff as well as the physicians performing the procedure due to the fact they arrive several hours prior to their scheduled surgery. All subjects will have enough time to ask questions about the study and the potential risks involved regardless of which venue they

PROTOCOL TITLE: Prospective Randomized controlled trial comparing liposomal bupivacaine to bupivacaine Interscalene blocks for total shoulder arthroplasty surgery

VERSION DATE: 7/6/2020

are consented. Any patient that refuses to participate in the study at any time point will be placed on a secured list to avoid duplicate attempts to recruit them.

Identification of Potential Participants: Patients will be identified by members of the treatment team in either the surgeon's clinic, pre-assessment clinic, or preoperative area. Patients who have opted out of research will not be asked to participate in the study. Patients will be approached to consent for the study by a surgeon, anesthesiologist, or member of the research team. Patients who agree to participate in the study will sign both a study consent and HIPAA authorization allowing the use of specified information contained in medical records for research purposes.

Recruitment Materials: N/A

Payment: No payment will be provided to patients.

12.0 Withdrawal of Participants

Withdrawal Circumstances: Subjects who have consented prior to the day of surgery and for some reason choose not to participate will be withdrawn and a notation will be made in the study records and these people will be considered screen failures. The surgeon may choose to withdraw the patient from the study prior to surgery for any medical reason or if they suffer a major life threatening adverse event.

Withdrawal Procedures: If the patient is withdrawn from study prior to the procedure, they will be noted in study records as screen failures. If they undergo the procedure and they decide they no longer want to be a part of the study or withdrawn by the physician, they will be withdrawn and no further data will be collected. This will also be noted in the study documentation.

Termination Procedures: If the study is terminated for any reason, or there is more than 5 % major adverse events the data that is already collected will be stored in a secure location only accessible to research personnel on this study. No further data will be collected if the study is terminated.

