5.0 Procedures Involved

Study Design: Level I randomized prospective outcomes study comparing two groups of patients. Patients will be assigned either to Liposomal Bupivacaine plus bupivacaine for an interscalene block or they will receive bupivacaine for an interscalene block injection.

Study Procedures: After consenting to the study (either in clinic or the PAC clinic) and completion of the preoperative process (per standard of care), a randomization scheme from a random number generator will be followed to ensure equal likelihood of group assignment. The patient will be placed in the supine position with the head of the bed elevated 30 degrees with standard ASA monitors applied. Sedation will be provided with midazolam 0-2mg and propofol 0-50 mg. The interscalene groove will be identified with the ultrasound. Using sterile technique, a 21g Nerve block needle will then be inserted and advanced under ultrasound guidance until it is in the interscalene groove. Once in the interscalene groove, 20 mL of local anesthetic will be injected, with 10mL deposited at the top of the brachial plexus and 10mL at the bottom. In the study group, 5 mL of each 0.5% bupivacaine and LB will be injected at each location.

PROTOCOL TITLE: Prospective Randomized controlled trial comparing liposomal bupivacaine to bupivacaine Interscalene blocks for total shoulder arthroplasty surgery

VERSION DATE: 7/6/2020

The control group will have 20mL of 0.5% bupivacaine divided between the injection sites. Patients would be required to take a dose of acetaminophen 975 mg oral, gabapentin 300 mg oral, and Celebrex 400 mg oral prior to surgery (per standard of care). The patient will be monitored (vital signs, respiratory status and oxygen saturation) in the preoperative area until he/she is brought into the operating room for their procedure. A working block prior to surgery will be confirmed via sensory testing of the shoulder.

All patients will undergo a standard induction with propofol 1.5-3.0 mg/kg, lidocaine 60-100 mg, ondansetron 4 mg, dexamethasone 10 mg and ketamine 0.25 mg/kg. An LMA or ETT will be placed and an opioid sparing technique will occur. Standardized maintenance will be a propofol infusion without neuromuscular blockers. 25-50 mcg of IV Fentanyl will be utilized for increases in heart rate greater than 20% or increases in systolic blood pressure above baseline.

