While in the hospital all patients will receive a standardized multimodal pain medication regimen. Acetaminophen 975 mg q6 hours, ibuprofen 600mg q6 hours and prn oxycodone 5-10 mg q4 hours or 2-4 mg hydromorphone oral every 4 hours. All patients will be discharged with 30-40 pills of 5 mg oxycodone or 30-40 pills of hydromorphone 2 mg with instructions to take 5-10 mg oxycodone for severe pain every 4 hours as needed or 2-4 mg every 4 hours hydromorphone as needed for severe pain. Patients will be instructed to start with the lower dose, but can repeat the dose if needed up to 10mg oxycodone or 4mg hydromorphone every 4 hours if needed.

Assessments: Post-operatively patients will be evaluated at 2 and 6 hours post-operatively by a blinded research staff. This person will not be aware of the patient's mode of analgesia. The patients will be contacted via in person assessment or via telephone at 24, 48, and 72 hours +/- 5 hours. Patients will be asked to rate their pain on scale of 0-10. The amount of opioids used by the patient will be recorded by study personnel as will any other adjuvant pain medication used. The time in phase 1 and phase 2 of PACU will be recorded. The patients will be asked at 72 hours post-injection if they would undergo an interscalene block with their medication again or if they would choose a different form of pain management (ex: higher doses of pain medications). Patients will fill out a Quality of Recovery Survey at 72 hours and 14 days, and be assessed for block related complications at this time. As part of the research, patients also will undergo diagnostic ultrasound of their diaphragm on POD 1. All complications will be recorded including:

- Failure of the block
- Wound infections
- Subsequent procedures
- Complications related to placement of the interscalene block including nerve injury, prolonged sensory loss greater than three days, prolonged arm weakness greater than three days
- Opioid related side effects of nausea and/or vomiting
- Local anesthetic toxicity as evidenced by seizures or cardiovascular collapse without other reasonable etiology

All data will be recorded on the Clinical Diagnostic Sheet and will then be given to the research coordinator for manual data entry. Data collection will continue until POD #14. At that time study participation will be terminated. Should patients be re-admitted to the hospital in the next two weeks (Up to POD 30) for pain, a notation will be made in study records.

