An analysis of the total cost of analgesics will be tabulated at the conclusion of the study to determine the most cost effective treatment option as this will be

PROTOCOL TITLE: Prospective Randomized controlled trial comparing liposomal bupivacaine to bupivacaine Interscalene blocks for total shoulder arthroplasty surgery

VERSION DATE: 7/6/2020

added into the cost of hospitalization including the number of days each patient spent in the hospital.

Blinding Procedure: A random number generator will be used to determine if the patient will have LB plus bupivacaine or bupivacaine for their interscalene block. The primary investigator will access the number generator in the pre-op area immediately prior to block placement. The website www.random.org will be used as the random number generator.

The research assistant in this study will be blinded to the method of analgesia for the patient. This person will not be responsible for any clinical testing and will record all data in the protected database daily. They will not have any access to the patients' clinical records or chart. **Any questions from the patient will be referred to the on-call resident or staff on call.**

Study Duration: We anticipate the study to take approximately 1 year from the date of enrollment of the first patient. Patients will be in the study for 14 days and then their chart monitored for up to 30 days post surgery. The data analysis should take one month after full enrollment of the study.

Individually Identifiable Health Information: This study involves the use of individually identifiable health information. Please see attached HIPAA authorization form.

Use of Radiation: N/A

Use of Center for Magnetic Resonance Research: N/A

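### Section 12.0 does not limit screen failure to patients without an allocation, and it ends data collection on physician withdrawal or termination even where the patient still consents

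*Combined protocol and SAP*

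**What the plan says.** **Screen failure.** Section 12.0 (Withdrawal Procedures) states: "If the patient is withdrawn from study prior to the procedure, they will be noted in study records as screen failures". Under Withdrawal Circumstances the surgeon may "withdraw the patient from the study prior to surgery for any medical reason or if they suffer a major life threatening adverse event".

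**Timing of allocation.** Section 5.0 (Blinding Procedure): "The primary investigator will access the number generator in the pre-op area immediately prior to block placement". The block is then placed and tested before surgery.

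**Meaning of procedure.** Section 12.0 does not define the word. In section 5.0 it means the operation: patients are monitored "in the preoperative area until he/she is brought into the operating room for their procedure". In section 11.0, on consent sought on the day of surgery, it could mean the block; the discussion there involves study personnel "as well as the physicians performing the procedure due to the fact they arrive several hours prior to their scheduled surgery".

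**End of data collection.** Once the procedure has been done, a patient's own decision to leave and removal by a physician get the same treatment: "withdrawn by the physician, they will be withdrawn and no further data will be collected". For termination: "No further data will be collected if the study is terminated".

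**What would otherwise be collected.** Sections 3.0 and 5.0 plan opioid use over 72 hours, pain scores to 72 hours, Quality of Recovery at 72 hours and 14 days, complications to day 14 and chart monitoring to day 30. The listed complications include "prolonged sensory loss greater than three days, prolonged arm weakness greater than three days".

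**Analysis.** Section 15.0 names no analysis set and no rule for missing outcomes; it leaves the analysis to the statistician, working from the protocol.

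**The concern.** A screen failure is normally someone who never entered the randomised comparison. Here the label depends on an undefined event that comes after allocation, so it can be given to a patient who has an assigned arm and may already have had the block. If that patient is then left out of the arm-by-arm account, the groups compared are no longer those that were randomised.

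The second rule treats a physician's decision to take a patient off study as if the patient had refused further data collection. A patient who still consents could be left with an incomplete 72-hour opioid total and no 72-hour or day-14 assessment. Complications defined as lasting more than three days cannot be established if collection stops before then. Termination does the same to everyone in follow-up, at a moment when safety information on treated patients may be most wanted.

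**Working it through.** **1. Does either meaning of procedure close the gap?** The sequence in section 5.0 is allocation, block, sensory test, operation.
- If procedure means the operation, a patient withdrawn between allocation and surgery is a screen failure although randomised and possibly blocked.
- If it means the block, the same holds between the draw and the injection, a short interval.

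Neither meaning excludes a randomised patient.

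**2. Does another section restore the data?** Sections 5.0 and 17.0 call for complications and safety data to be recorded, and section 5.0 for follow-up to day 14 and chart monitoring to day 30. None says that this continues after physician withdrawal or termination, so these general statements do not override the specific instruction in section 12.0.

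**3. The plan's own allowance.** Section 15.0 needs 70 patients (35 per group) for 80% power. Section 10.0 consents 90, expecting 20% drop-out or loss. 70 / (1 − 0.20) = 87.5, rounded up to 88, close to the stated 90. Section 23.0 instead describes the 90 as screened in order to enrol 70. It is therefore unclear whether loss after randomisation is covered.

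**4. Power if loss is unrelated to outcome.** The plan gives no significance level, effect or SD. Assuming a two-sample t-test at two-sided 0.05, 35 per group with 80% power implies a difference of 0.68 SD. The documents give no withdrawal rate; up to 4 lost per arm is an assumption.

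| Reading | Analysed per arm | Power |
|---|---|---|
| 35 is the number before loss | 35 v 35 | 80% |
| 4 lost from one arm | 31 v 35 | 77% |
| 4 lost from each arm | 31 v 31 | 75% |
| Allowance covers loss: 90 × 0.80 = 72 | 36 v 36 | 81% |
| 90 randomised (45 per arm), 4 lost from each | 41 v 41 | 86% |

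**5. False positives if loss is related to opioid use (assumed).** 40,000 simulated trials, 35 per arm, no true effect, pooled t-test at two-sided 0.05. Patients are lost at random from the top 12 of 35 opioid users. The normal column also holds for log-normal data analysed on the log scale; the last column is log-normal data (log-SD 0.8) left untransformed.

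| Lost | Normal or log scale | Untransformed |
|---|---|---|
| None | 5.0% | 4.4% |
| 1, one arm | 5.2% | 4.5% |
| 2, one arm | 5.7% | 4.9% |
| 3, one arm | 6.7% | 5.7% |
| 4, one arm | 8.4% | 6.9% |
| 3 v 1 | 5.7% | 4.8% |
| 4 v 4 | 4.9% | 3.4% |

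Loss of 1 to 4 random patients from one arm leaves the rate at 4.9 to 5.1% (normal or log scale) or 4.3 to 4.5% (untransformed).

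**6. Patients affected by a termination.** Patients before day 14 = (number enrolled / days of enrolment) × 14, assuming even enrolment. Section 5.0 gives about 1 year (365 days); section 23.0 gives 3 months (91 days). Section 15.0 counts 30 pilot patients plus 40 more, so 40 is the low end; 90 is the high end.

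| Patients | Over 1 year | Over 3 months |
|---|---|---|
| 40 | 40/365 × 14 = 1.5 | 40/91 × 14 = 6.2 |
| 70 | 70/365 × 14 = 2.7 | 70/91 × 14 = 10.8 |
| 90 | 90/365 × 14 = 3.5 | 90/91 × 14 = 13.8 |

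So about 2 to 14 treated patients would miss the day-14 assessment. With 3 days in place of 14, about 0.3 (40/365 × 3) to 3.0 (90/91 × 3) would be inside the 72-hour window.

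**The case against.** The strongest case is that this is a small wording matter.

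- **A label is not an exclusion.** Noting someone as a screen failure does not say the patient is dropped from analysis. This stands. But with no analysis set in section 15.0, nothing says such patients are kept in.
- **The exposed interval is brief.** Surgeon withdrawal before surgery can affect a randomised patient only between the draw and the operation. This stands, and limits the likely number.
- **The power cost may be nil.** If the 20% in section 10.0 covers these losses, power stays at or above 80%. This stands on that section's wording; section 23.0 reads differently.
- **Nothing points to selective loss.** The stated grounds are a medical reason before surgery or a major life-threatening event, not pain or opioid use. This stands, although the later provision for withdrawal by the physician gives no grounds at all.
- **Termination stops both arms.** No difference by arm is claimed; the loss is of follow-up, not of comparability.
- **The missing analysis set belongs to section 15.0.** Fair, but a sentence in section 12.0 settles it for these patients.

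A reader might go further and infer that the opioid comparison will be biased, perhaps because section 5.0 describes blinding only of research staff. That shows opportunity, not that physicians would withdraw patients by arm or by opioid use. A reader might also infer that data already collected are discarded, or that part-complete opioid totals would be counted as full 72-hour totals. No section says either.

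**Conclusion.** The point holds as a cheap improvement. Section 12.0, followed as written, allows randomised patients to be recorded as screen failures, and it ends follow-up of treated patients who may still consent. No other section prevents this.

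The size is modest and depends on assumptions. How often it would happen is unknown. Outcome-unrelated loss of up to 4 per arm takes power from 80% to 75% at worst, and costs nothing if the 20% allowance applies. Inflated false positives, about 5 to 8% for 1 to 4 top-third users lost from one arm, require loss that is both related to opioid use and unequal by arm; the documents do not predict that, and balanced loss does not produce it. The firmest consequence is for follow-up: a termination would leave about 2 to 14 treated patients without the day-14 assessment, assuming even enrolment of 40 to 90 patients over 1 year or 3 months.

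**What to change.** Amend section 12.0 as follows.

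(a) Define procedure, and limit screen failure to patients for whom no allocation was drawn.

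(b) Keep every randomised patient in the assigned group for analysis, and report by arm, with reasons, any who have no outcome.

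(c) Separate physician withdrawal from withdrawal of consent. Continue the planned opioid, pain, recovery and adverse-event collection to day 14, and chart review to day 30, unless the patient withdraws consent to data collection.

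(d) On termination, complete the planned data collection for patients already treated who still consent.

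The cost is protocol wording and a few extra calls or chart reviews (about 2 to 14 patients at a termination), with no added patients. Items (c) and (d) are subject to what the consent form and HIPAA authorisation permit, which cannot be checked here. No change is proposed to when clinicians withdraw patients or to the 5% termination rule.

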4.0 Study Interventions/Investigational Agent(s)

Description: LB is a long acting local anesthetic. It is liposome encapsulated bupivacaine which allows for prolonged release of bupivacaine over a 72-hour period. Bupivacaine is a medium acting local anesthetic which provides between 6 and 24 hours of analgesia when used in a peripheral nerve block. Both medications are standard of care for use in interscalene blocks here at the U of MN. Acetaminophen is a medication used to treat pain, gabapentin is a gabapentinoid which is used to treat postoperative pain, and Celebrex is a selective COX-2 inhibitor also used to treat pain.

Drug/Device Handling: The LB will be stored in a locked pyxis fridge in a box labeled Liposomal Bupivacaine. The anesthesiologists in charge of regional anesthesia the day the procedure will be informed will write the order for dispensing the medication and the block per standard of care. It will be retrieved by the PI and sub I's for use in the interscalene blocks.

Biosafety: Per standard of care

Stem Cells: N/A

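### Section 12.0 ends all research data collection at a study stop, and when a physician withdraws a treated patient, so patients already blocked lose the rest of their safety follow-up

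*Combined protocol and SAP*

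**What the plan says.** The stop rule is in section 12.0 (Withdrawal of Participants), under Termination Procedures. The trigger reads "If the study is terminated for any reason, or there is more than 5 % major adverse events". Data already held are then to be stored securely, and the rule closes with "No further data will be collected if the study is terminated".

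Withdrawal Procedures, in the same section, covers people who have undergone the procedure. Whether they leave by their own choice "or withdrawn by the physician, they will be withdrawn and no further data will be collected". Withdrawal Circumstances lets the surgeon withdraw a patient before surgery "for any medical reason or if they suffer a major life threatening adverse event".

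The follow-up that would be cut short is in section 5.0 (Procedures Involved):

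- Contacts are at 24, 48 and 72 hours, each within 5 hours either way.
- At 72 hours and 14 days patients complete the recovery survey "and be assessed for block related complications at this time".
- "Data collection will continue until POD #14", and charts are then checked to day 30.
- The complications to be recorded include "prolonged sensory loss greater than three days, prolonged arm weakness greater than three days".

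Section 4.0 says that the liposomal product "allows for prolonged release of bupivacaine over a 72-hour period".

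**The concern.** After a stop for harm, the study has to say how many patients were harmed, in which arm, and whether they recovered. The rule as written ends observation at that moment. Sensory loss or weakness lasting beyond three days cannot be established before day 3. The last of the daily contacts falls at about 72 hours, so the 14-day assessment is in effect the only scheduled one that can identify these complications. A stop would cancel it for everyone treated in the preceding two weeks. Later analysis cannot recover data that were never collected.

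The single-patient rule has the same flaw on a smaller scale. A patient's own decision to leave is a consent reason to stop collecting data. A physician's decision to withdraw a treated patient is not, yet section 12.0 treats the two alike.

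**Working it through.** **Is there an exception elsewhere?** Four places could hold one.

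- Section 5.0, Assessments, sets follow-up to day 14. It does not say that this survives a stop.
- Section 5.0, Study Duration, sets the chart check to day 30. It makes no exception either.
- Section 17.0 sends data to the safety committee monthly and lets it make recommendations. It sets no follow-up after a stop.
- Section 19.0 covers care and billing for injury, not data.

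So the rule in section 12.0 stands alone.

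**The plan's own figures.** The plan gives no number of patients in follow-up at a stop. Its enrolment figures are consistent. Section 15.0 has 30 pilot + 40 additional = 70. With the 20% loss in section 10.0, 70 / 0.80 = 87.5, so 88, against 90 stated.

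**Inputs.**

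- Patients accruing: 40 after the pilot (section 15.0), or 70 (section 23.0, which pairs 70 with three months).
- Accrual time: three months = 91.3 days (section 23.0), or about one year = 365.25 days (section 5.0, Study Duration).
- Windows: 3, 14 and 30 days.
- Assumption: patients accrue at a steady rate. A stop early in enrolment would affect fewer.

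**Formula.** Expected patients inside a window at the stop = N × window / accrual days. Example: 40 × 14 / 91.3 = 6.1.

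| N, accrual | within 72 hours | within 14 days | within 30 days |
|---|---|---|---|
| 40, 3 months | 1.3 | 6.1 | 13.1 |
| 70, 3 months | 2.3 | 10.7 | 23.0 |
| 40, 1 year | 0.3 | 1.5 | 3.3 |
| 70, 1 year | 0.6 | 2.7 | 5.7 |

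Of those inside 14 days, (14 − 3) / 14 = 79% are already past 72 hours. They have had the daily contacts and the first block-complication assessment. They lose the day-14 assessment and the chart check.

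**Late complications missed, given a stop** = patients inside 14 days × rate. Section 13.0 puts nerve injury below 1%; 5% is an assumed higher rate for all late block complications.

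- At 1%: 1.5 × 0.01 = 0.02, up to 10.7 × 0.01 = 0.11.
- At 5%: 1.5 × 0.05 = 0.08, up to 10.7 × 0.05 = 0.54.
- For the largest cell to reach one missed event, the rate would have to be 1 / 10.7 = 9.3%.

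**Chance of a stop.** The protocol gives neither a denominator nor a schedule for the 5% criterion. Assume that it is applied monthly to all treated patients including the pilot, and that 40 new patients accrue. An exact binomial recursion for events / n > 0.05 then gives the following.

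- Three months, looks at 43, 57 and 70 patients: 2% of trials stop at a true major-event rate of 1%, and 11% at a rate of 2%.
- One year, 12 looks from 33 to 70 patients: 6% and 20%.

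**Primary outcome.** Only patients inside 72 hours can lose part of the opioid total. That is 0.3 to 2.3 patients.

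**The case against.** The strongest reply is that the loss is very small. With 40 patients, a 1% late-complication rate and a 1% major-event rate, expected missed events per trial are 6.1 × 0.01 × 0.02, or 1.5 × 0.01 × 0.06. Both come to about 0.001 if the two rates are independent. Section 23.0 also gives about 300 arthroplasties a year, or 75 a quarter. Three-month accrual would therefore need 40 / 75 = 53% or 70 / 75 = 93% of all cases, and the one-year end of the range is at least as credible. Both treatments are described as standard care at the site, and the committee could recommend continued follow-up at a stop.

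All of this stands as to size, and it limits how much weight the point deserves. It does not defend the rule. A stop for harm is exactly the case in which a 1% rate and independence are in doubt. A committee recommendation would also have to override the protocol's own text.

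A reader might infer three stronger points that the documents do not support.

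- *That every patient in the window loses the whole 14-day follow-up.* They lose only what remains of it, which for about four in five is the day-14 assessment and the chart check.
- *That a patient with a life-threatening event after the block will be withdrawn and the outcome lost.* The wording of that ground most naturally refers to the time before surgery, and withdrawal is at the surgeon's discretion. The paragraph that does cover treated patients gives no ground for physician withdrawal.
- *That the missing patients could hide a much higher major-event rate.* The protocol does not class prolonged numbness or weakness as major adverse events, so the late complications at issue may not count toward the 5% criterion at all.

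**Conclusion.** The concern holds as a cheap improvement to the safety data. Section 12.0 ends research data collection at any termination and when a physician withdraws a treated patient, and nothing elsewhere exempts patients already blocked. About 2 to 11 patients would lose the remainder of their 14-day follow-up at a stop, and about 3 to 23 would be inside the 30-day chart window. The spread arises because the documents give two accrual periods and two enrolment numbers. Both ranges assume steady accrual.

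The consequence is modest. Clinical care is not affected, a stop is unlikely at low event rates, and the primary comparison would lose part of the data on about two patients at most. Expected missed late complications are at most about 0.1 at the protocol's nerve-injury rate and about 0.5 at an assumed 5%. The point concerns the quality of the safety record after a stop. It does not show that the trial is unsafe or its main result unreliable.

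**What to change.** Two edits to section 12.0.

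1. Replace the last sentence of Termination Procedures with: *On termination, enrolment and study blocks stop. Patients already blocked complete their remaining 24-, 48- and 72-hour contacts, the 14-day assessment and the 30-day chart review, unless they withdraw consent.*
2. In Withdrawal Procedures, separate the two routes out of the study: *A patient withdrawn by the physician after the block stays in follow-up on the same schedule. Data collection stops only if the patient withdraws consent.*

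If the consent form repeats the present rule, change it to match.

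There is no cost unless a stop or withdrawal occurs. After a stop, the upper limit is four contacts per patient in the window: 1.5 × 4 = about 6, up to 10.7 × 4 = about 43. The real number would be lower, because most of these patients need only the day-14 contact. Staff must remain available for 14 days after a stop, and for 30 days for the chart review. An order to cease all contact would still take precedence.
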